## 1.0 BACKGROUND

### 1.1 The natural history of craniopharyngioma

Craniopharyngiomas, which occur at an average age-adjusted incidence rate of 0.18 per 100,000, are epithelial tumors that arise in the pituitary stalk along the path of the craniopharyngeal duct. There are two main subtypes of craniopharyngiomas, the adamantinomatous form that is more common in children and the papillary form that predominantly occurs in adults. Located in or above the sella turcica, these tumors grow adjacent to the optic chiasm and often extend to involve the hypothalamus, cranial nerves, the ventricular system, visual pathways and major blood vessels at the base of the brain. Craniopharyngiomas can cause profound clinical sequelae both in the pediatric and adult populations, both through mass effect at presentation and through morbidity of treatment. At initial presentation, a broad range of signs and symptoms can be observed. Visual deficits, neuroendocrine deficiencies and severe headaches are common. Attempted surgical resection is usually the initial treatment of craniopharyngioma, but because these tumors adhere to critical brain and vascular structures, incomplete resection is common. Incompletely excised tumors have a propensity to recur, frequently with cysts, with firm adhesions between the recurrent tumor and the surrounding structures such that curative surgery is exceedingly difficult. Either the cystic, solid or both components, of craniopharyngiomas can cause significant symptomatic mass effect. As a result, most patients suffer lifelong sequelae that include panhypopituitarism, visual defects, impaired intellectual function and wide-ranging hypothalamic dysfunction leading to sleep disorders, abnormal thermo-regulation, and diabetes insipidus as well as hyperphagia and uncontrollable obesity. Radiation therapy, often used as an adjunct after surgery, can contribute to these complications. The debilitating long-term morbidities can have significant psychosocial impact on patients. No effective treatment besides surgery and radiation is known for craniopharyngiomas, and incomplete knowledge of the molecular mechanisms that drive craniopharyngiomas has hampered the development of targeted therapies for this tumor.

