### 3.3.3 Prior treatment

- Cohort A: No prior therapy received other than surgery.
- Cohort B: Prior radiation therapy required (any type of prior radiation is allowed)
  - For patients treated with external beam radiation therapy, interstitial brachytherapy or radiosurgery, an interval of  $\geq 3$  months must have elapsed from completion of radiation therapy to registration
  - Recovered to CTCAE grade 1 or less toxicity attributed to radiation with exception of alopecia and fatigue.
- For patients enrolling on Cohort A or Cohort B:
  - For patients treated with surgery, an interval of  $\geq 21$  days must have elapsed prior to registration.
  - No prior treatment with BRAF or MEK inhibitors.
  - Steroid dosing stable for at least 4 days prior to registration.

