- \*\*\* Patients who progress or who do not progress within 2 years from registration, will be followed for survival every 6 months, for a maximum of 5 years from registration (step 1). Patients discontinuing for reasons other than progressive disease will be followed for progression every 16 weeks (+/- 4 weeks) until they have reached 2 years post-registration or until documented progression (whichever comes first), then followed for survival every 6 months, for a maximum of 5 years from registration (Step 1). See also [Section 12.0](#).
- 1 History & physical should include neurologic exam and assessment of endocrine therapy (including dosage and type the patient is receiving).
- 2 To be completed after pre-registration and  $\leq 21$  days prior to treatment, see [Appendix I](#).
- 3 Solicited AEs are to be collected starting at baseline. Routine AEs are to be collected starting after registration. See [Sections 9.1](#) and [9.2](#). See also AEs of special interest in [Section 9.3](#). See [Section 9.4](#) for expedited reporting of SAEs.
- 4 Albumin, alkaline phosphatase, total bilirubin, bicarbonate, BUN, calcium, chloride, creatinine, glucose, potassium, total protein, SGOT[AST], SGPT[ALT], sodium and CPK. Glucose must be fasting (i.e., 8 hours or more fast).
- 5 For women of childbearing potential. Must be done  $\leq 7$  days prior to registration and  $\leq 7$  days prior to initiation of vemurafenib and cobimetinib
- 6 See [Sections 4.3](#), [4.4](#) and [6.2](#) for central review submission.
- 7 Scans can include either: 1) MRI Brain or 2) CT Brain. CT should ONLY be used for patients unable to undergo MR imaging because of non-compatible device or life-threatening gadolinium allergy. Also see [Section 11.0](#). Supporting documentation is to be submitted, per [Section 6.1.1](#). **All MRIs must be performed per [Appendix II](#) and submitted to IROC Ohio. Response assessment should include assessment of all sites of disease.** Baseline scan should be submitted to IROC within 14 days after patient registration per [Section 6.3](#). Any images required per footnote E or that are part of clinical care should be submitted to IROC Ohio within 14 days after acquisition per [Section 6.3](#).
- 8 Oxygen saturation should be assessed at rest and after 1 minute walk. Dose modifications for hypoxia should be followed per [Section 8.2.2.15](#).

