#### 8.1.12 QT prolongation: Chronic concomitant treatment with drugs that are known to prolong the QT interval/are associated with Torsades should be avoided, as vemurafenib can cause QT prolongation and arrhythmia. See [REDACTED] (registration required but is free).

- 8.1.13 Radiation recall:** Vemurafenib has been reported to cause radiation recall. For patients who develop CNS toxicity and were previously irradiated for craniopharyngioma, consider performing MRI brain to evaluate.
- 8.1.14 Malignancy:** Both vemurafenib and cobimetinib are associated with skin malignancies. Patients should report any new or suspicious skin lesions promptly, and have skin exams per [Section 5.0](#). In addition, vemurafenib is associated with RAS-related malignancies, and any suspicious symptoms should undergo prompt workup. In addition, vemurafenib is associated with the formation of colon polyps, and patients should follow national guidelines for colon screening.
- 8.1.15 Rash:** Both agents are associated with rash and cobimetinib is associated with photosensitivity. Patients should avoid sun exposure and practice good skin care. Consider dermatology consult as needed in the setting of rash.
- 8.1.16 Ocular toxicity:** Vemurafenib is known to cause uveitis, and cobimetinib is known to cause retinopathy. In addition, due to the location of the tumor, patients with craniopharyngioma are known to have visual field defects. Regular eye exams should be performed as per [Section 5.0](#), and patients should report any visual changes promptly. Consider treatment with steroids for uveitis. Serous retinopathy may be treated with topical corticosteroid eye drops.
- 8.1.17 Bleeding:** Cobimetinib leads to an increased bleeding risk. Hemorrhage, including major hemorrhages, defined as symptomatic bleeding in a critical area or organ, can occur with cobimetinib. In clinical studies with cobimetinib, events of cerebral hemorrhage, GI tract hemorrhage, reproductive tract hemorrhage, and hematuria have been reported. Patients on anticoagulation should undergo increased frequency of monitoring while on treatment.
- 8.1.18 Pneumonitis:** Cobimetinib has been associated with pneumonitis. In the setting of suspected pneumonitis, consider CT scan, PFTs, pulmonary consult, and bronchoscopy, and consider treatment with steroids or referral to pulmonary and infectious disease specialists.

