## 9.0 ADVERSE EVENTS

The prompt reporting of adverse events is the responsibility of each investigator engaged in clinical research, as required by Federal Regulations. Adverse events must be described and graded using the terminology and grading categories defined in the NCI's Common Terminology Criteria for Adverse Events (CTCAE), Version 4.0 for dose modifications and adverse event reporting through Rave. However, CTCAE v5.0 must be used for serious AE reporting through CTEP-AERS as of April 1, 2018. The CTCAE is available at [REDACTED] Attribution to protocol treatment for each adverse event must be determined by the investigator and reported on the required forms. Please refer the NCI Guidelines: Adverse Event Reporting Requirements for further details on AE reporting procedures.

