### 9.1 Routine adverse event reporting

Adverse event data collection and reporting, which are required as part of every clinical trial are done to ensure the safety of patients enrolled in the studies as well as those who will enroll in future studies using similar agents. Adverse events are reported in a routine manner at scheduled times according to the study calendar in [Section 5.0](#). For this trial, the form "Adverse Events: Solicited" is used for routine AE reporting in Rave.

**Solicited Adverse Events:** The following adverse events are considered "expected" and their presence/absence should be solicited, and severity graded, at baseline and for each cycle of treatment.

CTCAE v4.0 Term	CTCAE v4.0 System Organ Class (SOC)
Blurred vision	Eye Disorders
Diarrhea	Gastrointestinal disorders
Fatigue	General disorders and administration site conditions
Alanine aminotransferase increased	Investigations
Aspartate aminotransferase increased	Investigations
CPK increased	Investigations
Photosensitivity	Skin and subcutaneous tissue disorders
Rash maculo-papular	Skin and subcutaneous tissue disorders

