### 13.4 Supplementary analysis plans

#### 13.4.1 Secondary Endpoints

- **Progression free survival:** progression free survival (PFS) will be estimated using the C Kaplan-Meier method within each cohort. Median PFSs and survival rates will be estimated with their 95% confidence intervals. No formal comparison will be made among the cohorts.
- **Toxicity:** As per NCI CTCAE v 4.0, the term toxicity is defined as adverse events that are classified as possibly, probably, or definitely related to study treatment. Toxicities will be evaluated via the ordinal CTCAE standard toxicity grading. Overall toxicity incidence as well as toxicity profiles by patient and treatment cohort will be explored and summarized. Frequency distributions, graphical techniques and other descriptive measures will form the basis of the analysis. No formal comparison will be made among the cohorts.
- **Response as defined by Enhancing Volume:** Response by Enhancing Volume will be estimated using Response Rate (RR) - where response rate is defined as the number of responses achieved during treatment with BRAF and MEK inhibitors divided by the total number of evaluable patients. For this endpoint, only decreasing volume in enhancing disease will count toward the criteria for response. The same thresholds for CR and PR as seen in Section 11.0 will be used. Point estimates will be generated for response rates within each cohort with corresponding 95% binomial confidence intervals (Duffy and Santner).
- **Response as defined by Non-Enhancing Volume:** Response by Non-Enhancing Volume will be estimated using Response Rate (RR) - where response rate is defined as the number of responses achieved during treatment with BRAF and MEK inhibitors divided by the total number of evaluable patients. For this endpoint, only decreasing volume in non-enhancing disease will count toward the criteria for response. The same thresholds for CR and PR as seen in [Section 11.0](#) will be used.

Point estimates will be generated for response rates within each cohort with corresponding 95% binomial confidence intervals (Duffy and Santner).

- **Overall Survival:** overall survival (OS) will be estimated using the Kaplan-Meier method within each cohort. Median overall survivals and survival rates will be estimated with their 95% confidence intervals. No formal comparison will be made among the cohorts.

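### Section 13.4.1 defines toxicity by attribution alone and makes no use of the baseline grades collected for the eight solicited adverse events

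*Combined protocol and SAP*

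**What the plan says.** **Collection.** Footnote 3 of the Study Calendar (Section 5.0) separates the two streams of adverse event data: "Solicited AEs are to be collected starting at baseline. Routine AEs are to be collected starting after registration". Section 9.1 lists eight solicited terms (blurred vision, diarrhea, fatigue, ALT, AST, CPK, photosensitivity, maculo-papular rash) and requires that "their presence/absence should be solicited, and severity graded, at baseline and for each cycle of treatment".

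**Analysis.** Secondary objective 2.2.2 is toxicity. Its analysis is one item in Section 13.4.1, where "the term toxicity is defined as adverse events that are classified as possibly, probably, or definitely related to study treatment". Events are graded by CTCAE, and "Overall toxicity incidence as well as toxicity profiles by patient and treatment cohort will be explored and summarized". Section 9.0 says who decides relatedness: "Attribution to protocol treatment for each adverse event must be determined by the investigator and reported on the required forms". Section 13.4.1 gives no treatment-emergent rule, no worsening rule and no comparison with baseline. The radiation-toxicity item in Section 13.4.2 and the stopping rule in Section 13.5.1 give none either. A later, detailed analysis plan is promised only for the exploratory endpoints in Section 13.4.2.

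**Condition at entry.** On presentation, Section 1.1 says: "Visual deficits, neuroendocrine deficiencies and severe headaches are common". Section 8.1.16 adds that "patients with craniopharyngioma are known to have visual field defects". For Cohort B, Section 3.3.3 requires: "Recovered to CTCAE grade 1 or less toxicity attributed to radiation with exception of alopecia and fatigue". Section 3.3.8 admits AST and ALT up to 2.5 times the upper limit of normal.

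**The concern.** The baseline grades exist so that a symptom already present can be told apart from one that starts or worsens on drug. The stated analysis does not draw that distinction. It asks only whether the investigator considers the event at least possibly related.

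That question is hardest to answer where the disease, its earlier treatment and the study drugs produce the same complaint. Fatigue is the clearest case. Section 9.5 lists it among the likely effects of both drugs, and Cohort B may enter with radiation-attributed fatigue above grade 1. AST and ALT increases also appear on both drug lists, and raised values are allowed at entry. With no control arm, the background rate of these symptoms cannot be seen anywhere else in the data.

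At stake is what the toxicity tables for objective 2.2.2 mean: a reader could take pre-existing morbidity for drug effect, in frequency and in grade.

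**Working it through.** **1. Is there a stated figure to reproduce?** Not for toxicity. The plan's only design figures concern response. An exact two-stage binomial calculation (9 patients, continue with at least 1 response; 16 patients, success with at least 3) gives a type I error of 0.0406 and power of 0.8864, against the stated 0.041 and 0.886. No adverse event input enters either figure, so this point cannot alter them.

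**2. Trace three patients through Section 13.4.1.** Suppose each has on-treatment fatigue rated possibly related.

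| Patient | Baseline grade | Worst grade on treatment | Counted under 13.4.1 | Worst grade above baseline? |
|---|---|---|---|---|
| X | 2 | 2 | grade 2 toxicity | no |
| Y | 0 | 2 | grade 2 toxicity | yes |
| Z | 1 | 2 | grade 2 toxicity | yes |

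The planned summary shows three identical events. The baseline grade separates X from Y and Z. If the investigator rates X's fatigue unrelated or unlikely, X drops out and no miscount occurs. The error therefore depends on attribution.

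**3. Unit of error.** Each cohort has 16 evaluable patients (Section 13.2.2). One miscounted patient moves a rate by 1/16 = 6.25 points.

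**4. Illustration only.** Let t be the rate that would be counted correctly, b the share of patients with the symptom at baseline, and m the chance that an unchanged baseline symptom is rated at least possibly related. Taking b as independent of t:

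reported rate = t + (1 − t) × b × m

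The documents give neither b nor m. I assume b = 20–60% and m = 25–50%, so b × m runs from 0.05 to 0.30. For t I borrow melanoma rates from Section 1.6.3, Tables 2 and 3. These cover all adverse events, not only related ones, so they are stand-ins.

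| Term and source of t | t | Excess, low: (1 − t) × 0.05 | Excess, high: (1 − t) × 0.30 | Reported rate |
|---|---|---|---|---|
| Fatigue, phase III combination arm | 32.3% | 0.677 × 0.05 = 3.4 points | 0.677 × 0.30 = 20.3 points | 36–53% |
| Fatigue, phase Ib, BRAF-inhibitor-naive | 69.8% | 0.302 × 0.05 = 1.5 points | 0.302 × 0.30 = 9.1 points | 71–79% |
| Blurred vision, phase Ib, BRAF-inhibitor-naive | 17.5% | 0.825 × 0.05 = 4.1 points | 0.825 × 0.30 = 24.8 points | 22–42% |

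With m = 0 the excess is zero in every row. The two fatigue rows differ only in the source of t, and the excess more than halves between them. The direction is fixed (upward), but the size is not something the documents can supply.

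**The case against.** The strongest reply is that attribution already does this work. Only related events count, the investigator must attribute each one, and the same site has graded the same term before the first dose. An investigator who sees unchanged fatigue can rate it unlikely to be related. This stands in part: it removes some of the problem, perhaps most of it. It does not remove all of it, because a rating of possible is enough, and for fatigue and AST/ALT both drugs are recognized causes.

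A second reply is that Section 13.4.1 allows profiles by patient, graphical techniques and other descriptive measures, which could include a shift table. That is also fair. A reader might infer that a worsening from grade 1 to 2 can never be told from a stable grade 2. The data do allow it, since both grades are collected; the plan simply does not commit to showing it.

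Other stronger readings are tempting and not supported:

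- *Tumor- or radiation-related vision loss will be tabulated as drug toxicity.* The solicited term is blurred vision. Visual fields are tested before registration and repeatedly afterwards, and their change over time has its own exploratory analysis (Section 13.4.2). Residual radiation toxicity other than fatigue and alopecia must be grade 1 or less at entry, so the radiation argument rests mainly on fatigue.
- *Both drugs are expected to cause every one of these symptoms.* For blurred vision, Section 9.5.1 puts the term among events with insufficient evidence of causation by vemurafenib; only the cobimetinib list in Section 9.5.2 carries it.
- *Cohort B's rates will be inflated more than Cohort A's.* Section 3.3 sets no limit on tumor- or surgery-related fatigue in either cohort, and no formal comparison of cohorts is planned. An imbalance is possible but not shown.

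**Conclusion.** The point holds as a gap in the stated toxicity analysis. Baseline grades of the eight solicited events are required, and no analysis text uses them. A pre-existing symptom that does not change but is rated at least possibly related would therefore be reported at its full grade, mainly for fatigue and to a lesser degree for blurred vision and AST/ALT.

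The conclusion rests on one condition: that some investigators rate unchanged symptoms as at least possibly related. If none do, the error is zero. If some do, each such patient adds about 6 points to a cohort rate. The percentages in the illustration should not be quoted as an estimate, because they depend on assumed prevalence and attribution and on melanoma rates that differ widely by study.

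The consequence is confined to a descriptive secondary endpoint. A reader might infer that early stopping is also at risk. The rule in Section 13.5.1 has no baseline reference either, but it needs related events of grade 4 or higher, so stable fatigue or blurred vision is unlikely to trigger it.

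**What to change.** Add to the toxicity item in Section 13.4.1: for each solicited adverse event, by cohort, report the number and proportion of patients whose worst on-treatment grade is higher than their baseline grade, with a table of baseline grade against worst on-treatment grade. Keep the planned summary of related events beside it.

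Both displays are needed. Worsening from baseline does not prove a drug effect in a single-arm trial, since the tumor may also progress, and a fluctuating symptom measured once at baseline and repeatedly afterwards will sometimes exceed its baseline grade by chance. Attribution covers some of that, and the shift table covers what attribution misses.

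The cost is one sentence in the plan and one set of tables per cohort. The grades are already collected under Section 9.1, and no visit, form, sample size or decision rule changes.

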### Pre-Study Testing Intervals

- To be completed  $\leq 28$  DAYS before registration:
  - All laboratory studies, history and physical, eye exam
  - Any scan which is utilized for tumor measurement per protocol.
- To be completed  $\leq 60$  DAYS before registration: Any baseline exams used for screening that are not utilized for tumor measurement.

	Prior to Registration*	Day 1 of each cycle (cycle is 28 days)*	Weekly on treatment	Every 2 cycles	Monthly on treatment	Post treatment followup**	Clinical & survival follow- up ***
Tests & Observations							
History and physical, weight, PS	X(1)	X(1)				X(1)	X(1)
Height	X						
Pulse, Blood Pressure	X	X					X
Registration Fatigue/Uniscale Assessment	X(2)						
Adverse Event Assessment	X(3)	X(3)				X(3)	X(3)
EKG		B					
Echo or MUGA		C					
O2 Saturation		X(8)					
Eye exam	A	A				A	
Skin Exam		D					D
Patient Medication Diary		X(9)					
Laboratory Studies							
Complete Blood Count, Differential, Platelets	X	X					
Electrolytes, Creatinine (BMP)			X (10)				
Endocrine evaluation (with labs as necessary per endocrine evaluation)					X		
Chemistry	X(4)	X(4)				X(4)	
Serum or Urine HCG	X(5)						
Staging							
Central review for eligibility (pathology/BRAF)	X(6)						
MRI/CT Brain	X (7)			E(7)		E(7)	E(7)

Correlative studies: For patients who consent to participate in A071601-ST1				
Tissue block or slides				Archival tissue at baseline, recurrence and progression for banking and correlative science, see Section 6.2 .
Whole blood samples				Whole blood at prior to treatment, Day 1 of Cycle 3 (+/- 3 days), end of treatment, recurrence and progression, see Section 6.2 .

- \* Labs completed prior to registration may be used for day 1 of cycle 1 tests if obtained  $\leq 14$  days prior to treatment. For subsequent cycles, labs, tests and observations may be obtained +/- 3 days from scheduled day of assessment. Radiographic windows are +/- 7 days from scheduled day of assessment (except prior to registration). A new cycle is defined by day 1 on which the patient starts drug for that cycle.
- \*\* Physical examination, adverse event assessment, medication diary, and chemistry are required 4 weeks (+/- 7 days) after the end of treatment. End of treatment is considered 4-5 cycles of treatment, or end of treatment with vemurafenib + cobimetinib.

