### 7.1 Vemurafenib + cobimetinib

Each cycle will consist of 28 days.

Agent	Dose	Route	Administration Days	Frequency
Vemurafenib	960 mg	P.O.	Days 1-28	Twice daily for 28 days
Cobimetinib	60 mg	P.O.	Days 1-21	once daily for 21 days, followed by 7 days off

For both arms, a cycle will be 28 days. Patients will be treated with vemurafenib 960mg po twice daily for 28 days, and cobimetinib 60mg po once daily for 21 days, followed by 7 days off. Dose modifications will be instituted for toxicity as per [Section 8.0](#). Contrast- MRI (or CT, see [Section 5.0](#)) will be performed every 8 weeks as outlined in [Section 5.0](#). See [Section 11.0](#) for response criteria.

If a dose of vemurafenib is missed, it can be taken up to 4 hours prior to the next scheduled dose. If a dose of cobimetinib is missed (i.e. 6 hours or more late), do not make up that dose; resume dosing with the next scheduled dose.

If cobimetinib meets criteria to be discontinued due to protocol dose modifications and vemurafenib does not, cobimetinib may be discontinued and patient may continue on single agent vemurafenib therapy.

If vemurafenib meets criteria to be discontinued due to protocol dose modifications and cobimetinib does not, vemurafenib may be discontinued and patient may continue on single agent cobimetinib therapy.

See complete dose modifications in [Section 8.0](#).

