#### 8.2.2.14 Rhabdomyolysis and CPK elevations

For **grade 4 CPK** elevation or CPK elevation and myalgia, withhold cobimetinib for up to 4 weeks. If improved to Grade 3 or lower, resume at the next lower dose level

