### *Pharmacokinetics*

Absorption: Bioavailability was 46% (90 CI 40-53%) in healthy subjects. A high-fat meal had no effect on cobimetinib AUC and Cmax after a single 20 mg cobimetinib dose in healthy subjects.

Distribution: 95% bound to human plasma proteins. Vd 806 L.

Metabolism: CYP3A oxidation and UGT2B7 glucuronidation.

Half-life, elimination: 44 hours (range 23-70).

Time to peak: Median time to Tmax 2.4 (range 1-24) hours.

Excretion: Feces (76%; ~7 as unchanged drug); Urine (~18%; ~2% as unchanged drug)

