## 13.5 Monitoring the study

### 13.5.1 Adverse event stopping rule

The stopping rule specified below is based on the current knowledge available. We note that the Adverse Event Stopping Rule may be adjusted in the event of either (1) the study re-opening to accrual or (2) at any time during the conduct of the trial and in consideration of newly acquired information regarding the adverse event profile of the treatment(s) under

investigation. The study team may choose to suspend accrual because of unexpected adverse event profiles that have not crossed the specified rule below.

The AE stopping boundaries are defined as follows: at any time, if we observe events considered at least possibly related to study treatment (i.e., an adverse event with attribute specified as “possible”, “probable”, or “definite”) within each cohort that satisfy the following criteria:

- if 2 or more patients in the first 10 treated patients (or 20% of all patients after 10 are accrued) experience a grade 4 or higher adverse event that excludes the following:
  - Hematologic Events
  - Any Asymptomatic Metabolic/Laboratory Abnormalities (excluding high CPK)

In the event that the boundary for the Adverse Event Stopping rule is crossed, the study team will consult with CTEP to evaluate the safety risk for participants of the trial and determine if a temporary suspension of accrual is needed.

We note that we will review grade 4 and 5 adverse events deemed “unrelated” or “unlikely to be related”, to verify their attribution and to monitor the emergence of a previously unrecognized treatment-related adverse event.

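### Every required on-treatment CPK draw nominally follows the 7-day cobimetinib break, so CPK toxicity and the CPK part of the stopping rule may be under-ascertained by an unknown amount

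*Combined protocol and SAP*

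**What the plan says.** The Section 5.0 calendar marks Chemistry before registration, on Day 1 of each cycle and after treatment. Footnote 4 makes it the only panel with CPK: "potassium, total protein, SGOT[AST], SGPT[ALT], sodium and CPK. Glucose must be fasting". The weekly row is "Electrolytes, Creatinine (BMP" and has no CPK. The timing notes add "For subsequent cycles, labs, tests and observations may be obtained +/- 3 days from scheduled day of assessment" and, for the end of therapy, "medication diary, and chemistry are required 4 weeks (+/- 7 days) after the end of treatment". The introduction to Section 5.0 also leaves on-treatment laboratory follow-up to institutional guidelines and clinical judgment.

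Section 7.1 gives "cobimetinib 60mg po once daily for 21 days, followed by 7 days off", with vemurafenib on all 28 days.

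Three parts of the plan use the CPK value:

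- Section 9.1 lists CPK increased among the solicited events, to be graded at baseline and in each cycle.
- Section 8.2.2.14 acts on grade 4 CPK, or on CPK elevation with myalgia: "withhold cobimetinib for up to 4 weeks. If improved to Grade 3 or lower, resume at the next lower dose level".
- Section 13.5.1 counts treatment-related events of grade 4 or higher. It leaves out haematologic events and "Any Asymptomatic Metabolic/Laboratory Abnormalities (excluding high CPK", so high CPK is counted even without symptoms.

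**The concern.** The documents attribute CPK elevation mainly to cobimetinib. In the phase III melanoma trial summarised in Section 1.6.3, it occurred in 29.9% of patients with cobimetinib and 2.9% without. Section 9.5.2 lists it as likely (>20%) for cobimetinib, and the vemurafenib list in Section 9.5.1 does not name it. The required draws nominally fall where cobimetinib exposure is lowest in the cycle.

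An asymptomatic elevation is visible only through a laboratory value. If it rises during Days 1-21 and subsides during the break, no required draw would show it. At stake are the CPK incidence reported under objective 2.2.2 and the CPK component of the stopping rule, which the authors deliberately kept.

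**Working it through.** The documents give no figure on this point: no operating characteristics for the adverse event rule and no sensitivity for Day 1 sampling. There is nothing to reproduce, so the check has three parts.

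**1. Schedule.** Cycle 1 Day 1 precedes any dose. With the +/- 3 day window, later Day 1 draws can fall from Day 26 of one cycle to Day 4 of the next. No CPK draw is required on Days 5-25. A patient who stops after 4 cycles has draws at C2D1, C3D1 and C4D1, then one after treatment. If treatment ends on Day 28 of cycle 4 (the last vemurafenib day), that draw comes 7 + 28 +/- 7 days after the last cobimetinib dose, which is 28 to 42 days.

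**2. Cobimetinib exposure at the draw.** Section 10.2 gives "Half-life, elimination: 44 hours (range 23-70" hours); Section 1.7.2 gives 48.8 h (23.1 to 80.0). The model is first-order decay with a bolus approximation, once daily on Days 1-21. The reference is the Day 21 trough, 24 h after the Day 21 dose.

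- Pre-dose Day 1 is 192 h after the Day 21 dose, or 192 - 24 = 168 h after that trough. The remaining share is 2^(-168/h).
  - h = 44: 2^(-3.82) = 7.1%
  - h = 48.8: 2^(-3.44) = 9.2%
  - h = 23: 0.6%; h = 80: 23%
- Early window edge, Day 26: 120 - 24 = 96 h after the trough. 2^(-96/h) gives 22% (h = 44) and 26% (h = 48.8), range 5.5-44%.
- Late window edge, pre-dose Day 4: three new doses plus the residual. At h = 44 the daily factor is r = 2^(-24/44) = 0.685.
  - New doses: r + r^2 + r^3 = 1.476.
  - Trough: about r/(1 - r) = 2.18.
  - Residual: 2.18 x 2^(-240/44) = 0.05.
  - Ratio: (1.476 + 0.05)/2.18 = 70%. At h = 48.8 it is 67%; range 59-89%.
- For comparison, at h = 44 and 48.8, pre-dose Day 8 is 92-93% and pre-dose Day 15 is 99-100% of the trough.

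**3. What incomplete detection could do to the rule (illustration only).** Let p be the true rate of related grade 4 CPK and s the share detected. For the first 10 patients in a cohort, with q = p x s:

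P(2 or more) = 1 - (1 - q)^10 - 10q(1 - q)^9.

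The documents give neither p nor s. Take p = 5% as an assumption:

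- s = 1, q = 0.05: 1 - 0.599 - 0.315 = 8.6%
- s = 0.75, q = 0.0375: 5.2%
- s = 0.5, q = 0.025: 1 - 0.776 - 0.199 = 2.5%

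This counts CPK alone. Other grade 4 or higher events also feed the rule, so these are not the rule's overall crossing probabilities.

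**The case against.** The strongest reply is that drug concentration is not CPK. The documents contain no CPK time course. Section 8.2.2.14 allows a hold of up to 4 weeks, which fits a grade 4 elevation that outlasts a 7-day break as well as one that does not. This stands: a reader might infer that CPK events will be missed or that toxicity will be understated, but the documents support only that this may happen.

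A second reply is that other routes exist. Section 5.0 allows extra tests, Section 13.5.1 counts events whenever they are found, and Section 10.2 asks patients to report weakness or muscle pain. Crossing the boundary leads to consultation with CTEP rather than automatic closure, and the team may suspend accrual without a crossing. These soften the consequence. They do not reliably reveal an asymptomatic elevation, because symptoms cannot prompt the test and discretionary testing varies by site. As for the 4-week allowance, it is a maximum, and after a final cycle 4 the next required draw is already at or beyond it.

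Third, the passages do not contradict one another; all can be followed together. That is correct. The gap is between what the calendar measures and what the rules rely on.

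Two further inferences should be resisted:

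- *That the argument covers AST and ALT, which share the panel.* Vemurafenib is given without a break, Section 1.7.1 reports near-constant exposure, and Section 8.2.2.2 reduces vemurafenib, not cobimetinib, after grade 3 transaminase events. Asymptomatic AST/ALT elevations are also outside the stopping rule.
- *That grade 4 CPK occurs in 10% or more.* Section 1.6.3 prints 10.2% under grade >3, but the same paragraph puts 65% of patients in that category. The phase Ib trial of the same combination reports 62.0% at grade 3 or higher and only 9.3% with any grade 4 event. The 10.2% is therefore probably grade 3 or higher, and the grade 4 rate is lower.

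**Conclusion.** The point holds for CPK and cobimetinib only. All required on-treatment CPK sampling nominally coincides with the cobimetinib minimum, and a final cycle 4 has no required CPK until 28-42 days after its last cobimetinib dose. CPK incidence under objective 2.2.2 and the CPK part of Section 13.5.1 may be under-ascertained, by an amount the documents do not allow to be estimated.

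The exposure figures rest on the documents' half-lives and a simple decay model. A draw late in the window is much less affected than one on Day 1. The stopping-rule figures rest on an assumed 5% rate and assumed detection shares. The type I error, power and sample size of the response design do not depend on this point. The change is worth making because it is cheap and the plan explicitly relies on the value.

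**What to change.** Reconcile the Section 5.0 calendar with Sections 9.1, 8.2.2.14 and 13.5.1. Add CPK alone, as adverse event ascertainment, to one weekly BMP draw already required while cobimetinib is being taken in each cycle, including cycle 4. Use a draw other than the one at Day 1. Keep the Day 1 panel. State that the solicited CPK event and the Section 13.5.1 count use the worst value in the cycle.

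The cost is one extra analyte per cycle on an existing draw, a calendar footnote and no new visit. Reported CPK rates may be higher, and more results will feed the existing CPK rule, so more of the holds it already calls for may follow. No dose or management rule is proposed. If the calendar stays as it is, the trial report should say that scheduled CPK was sampled after the cobimetinib break.
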